### Secondary objectives

- To investigate changes in adverse event-related quality of life using patient-reported questionnaires (PRO-CTCAE, Skindex 16).
- To investigate the safety/tolerability of benralizumab in patients with eosinophil-related cutaneous adverse events.
- To investigate the need for supportive medications (corticosteroids, antihistamines, immunosuppressants) in patients treated with benralizumab.
- To investigate the effect of benralizumab on subsequent planned cycles of checkpoint inhibitors (CPIs), or targeted therapies.
- To compare the effect of benralizumab on corticosteroid naïve and corticosteroid dependent/refractory ercAEs.

- To correlate the percent reduction in blood absolute eosinophil numbers and skin histology with clinical response to benralizumab.
- To investigate change in body surface area (BSA) of ercAE to quantify change in affected area in response to benralizumab over time.
- To investigate relative dose intensity (RDI) and compliance of patients' culprit anticancer therapy for the duration of the trial.

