**Missed doses will not be made up.**

## 11.0 EVALUATION DURING TREATMENT/INTERVENTION

Study Procedures	Screening Visit (-7 days to Day 1) 	Week 0/ Day 1	Week 2/ Day 14 (+/- 3 days)	Week 4/ Day 28 (+/- 3 days)	Week 8/ Day 56 (+/- 3 days)	Week 16/ Day 112 (+/- 7 days) 	Week 24/ Day 168 (+/- 7 days) 	Week 32/ Day 224 (+/- 7 days) 	4 Weeks post-last dose (+/- 7 days)
Informed Consent	X 								
Demographics	X								
Medical history	X								
Concomitant medication review	X	X	X	X	X	X	X	X	X
Serum pregnancy test, per SOC and if applicable	X 								
Skin biopsy 	X			X					
CBC with differential	X	X	X	X	X	X	X	X	X
Comprehensive Metabolic Panel	X								
Physical exam and vital signs (HR, BP, weight, and temperature)	X								
Skin Exam (prior to Benralizumab administration)		X		X	X				
ECOG Performance Status (Appendix C)	X								
Total body photography	X	X		X	X				
Eosinophil-related Adverse Event Grading (CTCAE v5.0) (Appendix A)	X	X	X	X	X	X	X	X	X
Research blood collection for biomarker analysis (IL-5 & MSD Panel)		X		X	X				

Adverse event evaluation	X	X	X	X	X	X	X	X	X
Patient self-assessment (PRO-CTCAE (Appendix D) & Skindex 16 (Appendix B)	X	X	X	X	X	X	X	X	X
RegiSCAR Scoring System for Diagnosing DRESS Syndrome		X							
Benralizumab 30mg SC administration		X		X	X	X	X	X	

SOC, standard of care.

1. Informed consent within 45 days prior to treatment.
2. Serum pregnancy test for WOCBP within 14 days prior to treatment.
3. The baseline skin biopsy will be obtained within 30 days of treatment start, if applicable per standard of care. The biopsy at day 28 will be RNB if the patient's symptoms are improving.
4. Assessments will continue as long as the patient continues receiving benralizumab (up to 32 weeks). If a patient discontinues benralizumab, they will move to the 4 weeks post-last dose follow-up visit.
5. Screening and Week 0/Day 1 visits can be combined as long as comprehensive metabolic panel, CBC w/ differential, and pregnancy test (if applicable) are resulted to confirm eligibility prior to first benralizumab injection.

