### 13.1 Criteria for Therapeutic Response/Outcome Assessment

Evaluation of ercAE by CTCAE v5.0

Response (R): Grade 2 or 3 event reduction to grade 0 or 1.

Nonresponding AE (nrAE): Grade 2 or 3 event that does not reduce to grade 0 or 1.

Progressive AE (pAE): Grade 2 event that increases by  $\geq 1$  grade in severity.

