## 14.0 BIOSTATISTICS

This is a single-center single-arm phase II study to evaluate the efficacy and safety of benralizumab for the treatment of eosinophil-related cutaneous adverse events (ercAE) in patients having grade 2/3 ercAE to various treatments (such as checkpoint inhibitors or targeted therapies) with blood eosinophil counts of at least .3 K/mcL.

The primary endpoint of efficacy is defined as the proportion of patients who have a reduction from CTCAE grade 2/3 eosinophil-related cutaneous adverse events to grade  $\leq 1$  following treatment with benralizumab. The study will be declared positive if  $\geq 70\%$  of patients have a reduction of grade 2/3 eosinophil-related cutaneous adverse events to grade  $\leq 1$  (between Week 0/Day 1 and Week 4/Day 28).

Data from medical oncology and other MSK visits will be collected at the last study visit for each patient and immune related adverse events with grade and attribution will be included in the final analysis.

Data analysis will be conducted by externally funded biostatistician (consultant), [name] of Augmentium Pharma Consulting Inc. The Consultant will serve to review, analyze, and assess data, documents and information provided from MSK, which shall be MSK's Confidential Information, and provide subsequent guidance in a format. The Consultant will also provide independent information to support MSK's clinical research activities. Additional projects that are beyond the scope of this WP will require a separate document executed in writing between the Parties. The Services shall be provided by Consultant at the direction and discretion of MSK and all deliverables or other materials produced by the Consultant shall be subject to Section 5 of the Agreement. The consultant will have access to participant PHI including name, demographics (DOB, age, gender, race, ethnicity), medical history (treatment start and end date and treatment information) and questionnaire responses. Details of this contract are available on the PIMS regulatory binder.

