#### **14.1 Populations for Analyses**

A total of 48 evaluable patients will be accrued to this study. Patients having a solid tumor or hematologic malignancy, grade 2/3 ercAE to various treatments and blood eosinophil counts of at least .3 K/mcL will be recruited from the medical oncology and dermatology clinics (Section 7.0). Patients will receive benralizumab treatment on Week 0/Day 1 and Week 4/Day 28, and will be assessed for efficacy at baseline Week 0/Day 1 (+/- 3 days), Week 2/Day 14 (+/- 3 day), Week 4/Day 28 (+/- 3day) and Week 8/Day 56 (+/- 3 days) (Section 4.2). If the second dose is missed, it will not be made up (Section 10.0). Patients can remain on study until progression of ercAE or unacceptable toxicity related to benralizumab up to 32 weeks (Section 4.2).

Patients will be considered evaluable as long as they receive at least one dose of benralizumab. Patients who are enrolled and removed from study before they receive their first dose of benralizumab will be considered inevaluable and will be replaced. Data analyses for the primary, secondary and exploratory endpoints will be based on 28 evaluable patients. Summary statistics will also be reported separately for patients removed from the study, including a summary of reasons for removal, their median duration in the study and range, mean and standard deviation of their eosinophil counts, and proportion of in ercAE categories at baseline and at all follow-up times prior to their removal from the study.

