**Secondary endpoints:**

**AE-related quality of life:** Quality of life will be assessed for all patients at Week 0/ Day 1, Week 2/Day 14, Week 4/Day 28 and Week 8/Day 56, Week 16/Day 112, Week 24/Day 168, Week 32/Day 224 and 4 weeks post-last dose using PRO-CTCAE and Skindex 16 (Appendix D). Prior to conducting analyses, we will evaluate questionnaire compliance. The amount of missing data across the PRO instruments will be summarized. A questionnaire will be considered complete if enough questions were completed to be a valid score. Since these instruments are broken into sections, completion of any section for a given adverse event will be considered complete information for that adverse event. Baseline characteristics of study participants with completed and incomplete QOL data will be compared in a descriptive manner. Mouth/throat sores, dry skin and itchy skin are reported on a 5-point scale, while rash, hives and sensitivity of the skin to sunlight are reported on a 2-point scale. These symptoms will be summarized using descriptive statistics. The proportion of patients with different levels of these symptoms will be assessed at each study time point along with exact binomial confidence intervals. A summary score for the Skindex-16 will be calculated for each participant at each time point. The total Skindex-16 score will be summarized for each study time point along with 95% confidence intervals.

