**Safety and tolerability of benralizumab:** This endpoint will be measured in terms of CTCAE v5.0 ercAE. The proportion of patients with different grade categories (0, 1, 2 etc) will be assessed at each study time point along with exact binomial confidence intervals. Patients progressing to grade 4 ercAE will be removed from the study (Section 12.0). The proportion of such patients at each time point will be reported. The proportion of patients having a reduction and the proportion having an increase in ercAE grade category will be reported.

**Need for supportive medication:** The proportion of patients requiring supportive medications such as corticosteroids, antihistamines and immunosuppressants will be reported at each time point along with exact binomial confidence intervals.

**Effect of benralizumab on subsequent planned cycles of checkpoint inhibitors (CPIs) or targeted therapies:** We will measure changes in blood eosinophil levels between baseline and cycles of various planned treatments for these patients, and report the mean, standard deviation, range and number of patients scheduled to receive different therapies.

**Effect of benralizumab on corticosteroid naïve and corticosteroid dependent/refractory ercAEs:** Corticosteroid naïve patients are those not receiving corticosteroids for 14 days since Week 0/Day 1 of benralizumab treatment. Corticosteroid dependent/refractory ercAEs are patients that are on prednisone 10mg a day or greater at the initiation of study. We will report the number of corticosteroid naïve and dependent/refractory ercAE patients, measure change in blood eosinophil levels between Week 0/Day 1 and Week 8/Day 56, report descriptive statistics such as mean, standard deviation and range in these groups of patients.

**Effect on eosinophil counts:** Changes in eosinophil counts will be calculated and reported as percent reduction +/- standard deviation. In addition to comparing baseline and end-of-study percent change in eosinophils, we will also compare percent changes across baseline ercAE categories and end-of-study ercAE categories. We will use regression models to examine the association between longitudinal measurements of percent change in eosinophils at Week 0/Day 1, Week 2/Day 14, Week 4/Day 28, and Week 8/Day 56, Week 16/Day 112, Week 24/Day 168, Week 32/Day 224 and 4 weeks post-last dose and longitudinal measurements of ercAE categories.

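### The safety and tolerability endpoint is measured only by ercAE grade, and Section 14 plans no summary of adverse events that are neither ercAEs nor immune-related

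*Combined protocol and SAP*

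**What the plan says.** Section 2.0 lists among the secondary objectives: "To investigate the safety/tolerability of benralizumab in patients with eosinophil-related cutaneous adverse events". The safety paragraph under Secondary endpoints in Section 14.1 puts this into practice: "This endpoint will be measured in terms of CTCAE v5.0 ercAE". Every summary it then names concerns ercAE grade: the proportion of patients in each grade at each time point with exact binomial intervals, the proportion progressing to grade 4, and the proportions whose grade falls or rises. Section 13.1 uses the same grade for efficacy: "Response (R): Grade 2 or 3 event reduction to grade 0 or 1".

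Data collection is wider than this.

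- The Section 11.0 schedule has a row "Adverse event evaluation", separate from the ercAE grading row and marked at every visit.
- Section 15.2 makes all AEs reportable whatever their cause until 30 days after the last dose. It has them recorded on the AE CRF with dates, grade and suspected relationship to study drug.
- Section 15.0 names CTCAE version 5 as the toxicity scale but describes no summary.

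Four provisions give partial cover.

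- Section 14.0, drawing on medical oncology and other clinic visits, says that "immune related adverse events with grade and attribution will be included in the final analysis".
- Section 14.1 describes patients removed from the study, "including a summary of reasons for removal".
- The quality-of-life paragraph covers patient-reported symptoms: "Mouth/throat sores, dry skin and itchy skin are reported on a 5-point scale", with rash, hives and sun sensitivity on a two-point scale.
- Section 15.2 provides an SAE line listing for the drug supplier at study end, for reconciliation.

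**The concern.** The objective asks how well benralizumab is tolerated. The endpoint answers with the grade of the skin condition that benralizumab is given to treat. A falling ercAE grade is efficacy, yet the plan would report it under safety and tolerability. A headache, sore throat or fever after an injection cannot change the endpoint.

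At stake is whether a stated secondary objective gets an answer. Section 1.0 describes a study of efficacy and safety, in patients continuing anticancer therapy rather than in the asthma population from which Section 15.0 takes its rates. The relevant data will be on the AE CRF, but with no planned summary, what is reported from them would be decided after the results are known.

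**Working it through.** The plan states no figure on this point, so there is none to reproduce. The check is mainly textual; the arithmetic only shows the scale.

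**Step 1: what the endpoint can contain.** Section 1.0 defines ercAEs as maculopapular rash, pruritus/urticaria, bullous pemphigoid or DRESS with raised eosinophils. Section 13.0 grades them by skin and subcutaneous AE term. The endpoint does go beyond the Week 4 primary response, because it includes worsening, grade 4 progression and later visits. It stays on the same scale, however, and non-cutaneous events such as headache, pharyngitis and pyrexia are not on it.

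**Step 2: where such an event could surface.** No paragraph of Section 14 summarises AE CRF events, SAEs or drug-related AEs as such. A non-cutaneous reaction could surface as a reason for removal (Section 14.1), as an event judged immune-related (Section 14.0), or as an SAE in the reconciliation listing (Section 15.2). The patient-reported items cover skin and mouth/throat symptoms and are analysed as quality of life. None of these tabulates adverse reactions to benralizumab.

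**Step 3: hypersensitivity.** Section 15.0 warns of hypersensitivity, including rash and urticaria, and says benralizumab should be stopped if it occurs. Section 15.2 has the investigator review any worsening skin reaction with this possibility in mind. Clinical handling is therefore specified, but no tabulation of the events is. Stopping the drug is also not the same as removal: under footnote 4 of the Section 11.0 schedule, a patient who stops moves to the visit 4 weeks after the last dose.

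**Step 4: scale.** The inputs are the Section 15.0 rates for benralizumab and placebo in asthma Trials 1 and 2. Section 14.1 accrues 48 evaluable patients but also says "Data analyses for the primary, secondary and exploratory endpoints will be based on 28 evaluable patients", so both sizes are shown. Expected patients = n × p; chance of at least one = 1 − (1 − p)^n; excess = n × (p − p_placebo).

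| Reaction (benralizumab; placebo) | n = 28: expected; chance of ≥1; excess | n = 48: expected; chance of ≥1; excess |
|---|---|---|
| Headache (8%; 6%) | 28 × 0.08 = 2.24; 1 − 0.92^28 = 0.903; 0.56 | 48 × 0.08 = 3.84; 1 − 0.92^48 = 0.982; 0.96 |
| Pharyngitis (5%; 3%) | 28 × 0.05 = 1.40; 1 − 0.95^28 = 0.762; 0.56 | 48 × 0.05 = 2.40; 1 − 0.95^48 = 0.915; 0.96 |
| Pyrexia (3%; 2%) | 28 × 0.03 = 0.84; 1 − 0.97^28 = 0.574; 0.28 | 48 × 0.03 = 1.44; 1 − 0.97^48 = 0.768; 0.48 |
| Hypersensitivity (3%; 3%) | 0.84; 0.574; 0 | 1.44; 0.768; 0 |

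The expected counts are all-cause, not drug-caused.

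**Step 5: precision of the absent table.** For zero events, the exact two-sided 95% upper limit is 1 − 0.025^(1/n): 12.3% at n = 28 and 7.4% at n = 48. For two events, the Clopper-Pearson intervals are 0.88% to 23.50% around 7.1% (2/28), and 0.51% to 14.25% around 4.2% (2/48).

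**The case against.** The strongest reply has five parts.

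1. Section 14.0 brings immune-related AEs, with grade and attribution, into the final analysis, and these are not confined to the skin. This stands and sets the limit of the point. A reader might infer that the plan counts no AE other than ercAEs and reports no attribution at all; Section 14.0 rules that out. The gap is AEs that are neither ercAEs nor immune-related.

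2. Skin worsening is a legitimate safety measure for this drug, since Section 15.0 names rash and urticaria among its hypersensitivity reactions. This also stands. Grade increase and grade 4 progression belong in the safety endpoint and should remain there.

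3. Suspected hypersensitivity is reviewed by the investigator and leads to discontinuation, so a recognised reaction is not meant to continue unnoticed. That stands for clinical care. It does not supply a count.

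4. The data exist and nothing prevents their being tabulated. True, but a table made without a plan is not a planned analysis of the objective.

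5. The numbers are small: the excess over placebo is at most about one patient per reaction at n = 48, and none for hypersensitivity. True. The point rests on the text, and the figures only illustrate it.

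**Conclusion.** The point holds in this form: safety and tolerability is measured only by ercAE grade, and Section 14 plans no summary of AEs that are neither ercAEs nor immune-related, although they are collected. Followed as written, the plan leaves the safety objective largely unanswered. It should be amended, but it does not touch the primary test or the success rule.

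In size, an all-cause table would be expected to show about 2.2 patients with headache, 1.4 with pharyngitis and 0.8 with pyrexia at n = 28, or 3.8, 2.4 and 1.4 at n = 48. This assumes that rates from 48-week asthma trials carry over to at most six doses over 32 weeks in patients on anticancer drugs, which the documents do not establish.

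Two stronger readings are tempting and unsupported. A reader might infer that patients are inadequately protected; SAE reporting (Sections 15.1 and 15.2) and committee monitoring (Section 16.4) run separately from this endpoint. A reader might also infer that the safety result would be biased towards looking favourable; nothing in the documents establishes a direction.

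**What to change.** Add to the safety paragraph in Section 14.1 a table from the AE CRF covering all patients given at least one dose, from first dose to 30 days after the last. It should show AEs and SAEs by CTCAE v5.0 term and worst grade per patient, all-cause and investigator-attributed, with exact 95% confidence intervals and a separate line for hypersensitivity events. Keep ercAE grade increase and grade 4 progression beside it as safety measures, and report ercAE grade reduction as efficacy.

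The cost is one standard table from data already collected, with no new visits or assessments. The downside is a little extra analysis and background events shown without a control arm. The table cannot isolate what the drug caused; it gives all-cause counts and the investigator's attribution.

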## 1.0 PROTOCOL SUMMARY AND/OR SCHEMA

This is a single-center, single-arm phase II study to evaluate the efficacy and safety of the anti-IL-5R $\alpha$  chimeric monoclonal antibody benralizumab for the treatment of eosinophil-related cutaneous adverse events (ercAEs) resulting from immunotherapies or targeted therapies. Forty eight (48) patients will be enrolled and the estimated time to completion is 2 years. The primary endpoint for the study is the percent reduction in CTCAE grade 2/3 eosinophil-related cutaneous adverse events to grade  $\leq 1$ . Eosinophil-related cutaneous adverse events are defined as maculopapular rash, pruritus/urticaria, bullous pemphigoid, or DRESS syndrome that are associated with blood eosinophil counts of at least .3 K/mcl. Secondary endpoints are safety and tolerability of benralizumab, calculated rash body surface area (BSA), relative dose intensity (RDI) of anticancer therapy, measurement of patient-reported quality of life, the ability to continue anticancer agents, effects on corticosteroid naïve and dependent/refractory ercAEs, the need for additional supportive care interventions (i.e. corticosteroids, antihistamines), and reduction in blood and skin eosinophils. An exploratory endpoint is analyzing eosinophils and Th2 immune pathway blood biomarkers ( IFN- $\gamma$ , IL-1 $\beta$ , IL-2, IL-4, IL-5, IL-6, IL-8, IL-10, IL-12p70, IL-13, TNF- $\alpha$ , tryptase) that correlate with benralizumab efficacy. Patients with a diagnosis of solid or hematologic cancers undergoing treatment with checkpoint inhibitors (CPIs) or targeted therapies with a grade 2/3 cutaneous adverse associated with blood eosinophil counts of at least .3 K/mcl will be treated with benralizumab 30mg once every 4 weeks for the first 3 doses (Week 0/Day 1, Week 4/Day 28, and Week 8/Day 56), followed by once every 8 weeks for 3 additional doses (Week 16/Day 112, Week 24/Day 168, and Week 32/Day 224). CTCAE v5.0 ercAE assessments will be done at baseline and then at Week 2/Day14, Week 4/Day 28, and Week 8/Day 56, Week 16/Day 112, Week 24/Day 168, Week 32/Day 224 and 4 weeks post-last dose. Patients may remain on study until ercAE progression or unacceptable toxicity from benralizumab for up to 32 weeks.

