## 6.0 CRITERIA FOR PARTICIPANT ELIGIBILITY

### 6.1 Participant Inclusion Criteria

- Patients must have pathologically or cytologically confirmed solid or hematologic cancers.  
OR
- Patient is receiving alpelisib for PIK3CA-Related Overgrowth Spectrum disorder.
- Female and male aged 18 to 85 years, inclusively, at the time of Week 0/Day 1 of treatment.
- Patients must have a therapy-related CTCAE grade 2/3 (See Appendix A) cutaneous adverse event defined as any cutaneous reaction listed below and blood eosinophil counts of at least .3 K/mcl.
  - Rash maculo-papular
  - Bullous dermatitis
  - Pruritus
  - Urticaria
  - Eczema
- Patients must plan to continue on culprit drugs (cancer patients).
- Patients planning to receive alpelisib indicated for PIK3CA-Related Overgrowth Spectrum disorder OR patients receiving immunotherapy and/or targeted therapy, including but not limited to the following agents, will be eligible for inclusion:
  - Immunotherapies: ipilimumab, nivolumab, pembrolizumab, avelumab, durvalumab, atezolizumab, tremelimumab.
  - Targeted therapies: trastuzumab, pertuzumab, alpelisib, osimertinib, everolimus, temsirolimus, sorafenib, regorafenib.
- Patients using topicals/orals for indication of skin rash/pruritus for at least 7 days should continue using these drugs for the study duration.
- Adequate bone marrow, liver and renal function:
  - Total bilirubin  $\leq$  1.5 x the upper limit of normal (ULN)
  - Alanine aminotransferase (ALT) and aspartate amino-transferase (AST)  $\leq$  2.5 x ULN ( $\leq$  5 x ULN for subjects with liver involvement of their cancer)
  - Alkaline phosphatase  $\leq$  2.5 x ULN ( $\leq$  5 x ULN for subjects with liver involvement of their cancer)
  - Serum creatinine  $\leq$  1.8 xULN or calculated creatinine clearance  $>45$  ml/min

- Platelet count > 50 K/mcL, hemoglobin (Hb) > 8 g/dL, absolute neutrophil count (ANC) > 1.0 K/mcL. Blood transfusion to meet the inclusion criteria will not be allowed.
- ECOG performance status 0-1 (see Appendix C).
- Subjects must be able to understand and be willing to sign the written informed consent form. A signed informed consent form must be appropriately obtained prior to the conduct of any trial-specific procedure.
- Female patients are authorized to participate if they meet the following criteria:
  - Women of child bearing potential must meet both of the following conditions:

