## 6.2 Participant Exclusion Criteria

- Concurrent use of another investigational drug or device for the ercAE (i.e., outside of study treatment) during, or within 4 weeks of treatment.
- Patients receiving prednisone  $\geq$  20mg a day.
- Known use of anti-IL-5 agents or biologics for the treatment of asthma which are known to decrease blood eosinophil levels.
- Patients cannot use new topicals or medications for indication of pruritus or skin rash
- Known history of anaphylaxis to biologic therapy
- A helminthic parasitic infection diagnosed within 24 weeks prior to the first treatment, that had not been treated with, or has failed to respond to, standard of care therapy.
- Known history of human immunodeficiency virus (HIV) infection or current chronic or active hepatitis B or C infection requiring treatment with antiviral therapy.
- Active infection that would impair the ability of the patient to receive study treatment.
- Women who are pregnant or breast-feeding.

- Any condition which, in the investigator's opinion, makes the subject unsuitable for trial participation.
- Receipt of live attenuated vaccines 30 days prior to the date of randomization
  - Receipt of inactive/killed vaccinations (e.g., inactive influenza) is allowed provided they were not administered within 1 week before/after any investigational product administration.
- Known history of allergy or reaction to the investigational product formulation

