### 13.2 Criteria for Study Endpoint Evaluability

Patients who are removed from the study prior to starting Benralizumab will be considered inevaluable and replaced. Patients who receive at least one dose of Benralizumab will be included in the evaluation of the primary objective if they have a post-therapy documented clinical response. Patients who progress and are placed on agents instead of or in addition to the culprit agents will be removed from the study. Patients who receive steroids at doses greater than prednisone 20mg a day or equivalent or other immunosuppressive agents to manage additional irAEs will be considered a failure for the primary endpoint.

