## 15.0 TOXICITIES/RISKS/SIDE EFFECTS

The dose of benralizumab is 30mg SC once every 4 weeks for the first 3 doses, followed by once every 8 weeks for 3 additional doses.. Doses will be delayed for clinically significant hematologic and non-hematologic toxicities that are related to protocol therapy according to the guidelines described in sections below. Dose adjustments for hematologic toxicity are based on the blood counts obtained prior to the day of treatment.

Most common adverse reactions (incidence greater than or equal to 5%) include headache and pharyngitis. Hypersensitivity reactions (e.g., anaphylaxis, angioedema, urticaria, rash) have occurred following administration of benralizumab. These reactions generally occur within hours of administration, but in some instances have a delayed onset (i.e., days). In the event of a hypersensitivity reaction, benralizumab should be discontinued.

Systemic or topical corticosteroids should not be abruptly interrupted or discontinued upon initiation of therapy with benralizumab. Reductions in corticosteroid dose, if appropriate, should be gradual. Reduction in corticosteroid dose may be associated with systemic withdrawal symptoms and/or unmask conditions previously suppressed by systemic corticosteroid therapy. Eosinophils may be involved in the immunological response to some helminth infections. Patients with known helminth infections were excluded from participation in clinical trials. It is unknown if benralizumab will influence a patient's response against helminth infections.

Treat patients with pre-existing helminth infections before initiating therapy with benralizumab. If patients become infected while receiving treatment with benralizumab and

do not respond to anti-helminth treatment, discontinue treatment with benralizumab until infection resolves.

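### The supportive-medication proportion does not separate baseline from new use, and two medication rules hold its rash/itch part near the entry level, so it is a poor measure of additional need

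*Combined protocol and SAP*

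**What the plan says.** Section 2.0 lists the objective as: "To investigate the need for supportive medications (corticosteroids, antihistamines, immunosuppressants) in patients treated with benralizumab". The protocol summary (Section 1.0) words the matching endpoint as *additional* supportive care.

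Section 14 turns this into one summary: "The proportion of patients requiring supportive medications such as corticosteroids, antihistamines and immunosuppressants will be reported at each time point", with exact binomial confidence intervals. It does not state the indication for the drug, a baseline reference, how dose changes count, or what distinguishes requiring a drug from taking it.

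Four other texts govern the same drugs:

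- Section 6.1, inclusion criteria: "Patients using topicals/orals for indication of skin rash/pruritus for at least 7 days should continue using these drugs for the study duration".
- Section 6.2, exclusion criteria: "Patients cannot use new topicals or medications for indication of pruritus or skin rash". No on-study period is stated.
- Section 15.0: "Systemic or topical corticosteroids should not be abruptly interrupted or discontinued upon initiation of therapy with benralizumab", and then "Reductions in corticosteroid dose, if appropriate, should be gradual".
- Section 13.2: "Patients who receive steroids at doses greater than prednisone 20mg a day or equivalent or other immunosuppressive agents to manage additional irAEs" count as failures for the primary endpoint, so the plan expects such use to occur on study.

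The schedule in Section 11.0 has a concomitant-medication review at every visit.

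**The concern.** The endpoint is meant to show whether patients on benralizumab need less, or no more, supportive treatment. Two entry rules limit movement in both directions. A patient whose rash clears is asked to stay on the drugs used at entry, and so may still be counted at Week 32. A patient who worsens without such drugs may not be allowed to start one, and so may never be counted.

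A flat proportion could then be taken as no sparing of supportive drugs, and a low rate of new use as benefit. Either pattern could come from the protocol's own rules. At stake is the interpretability of a stated secondary endpoint. The primary endpoint is not affected.

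**Working it through.** The plan gives no expected rate, sample size or power for this endpoint, so there is no figure to reproduce. The check is to write the count out and see which terms the rules leave free.

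**Notation.** None of these values is given in the documents.

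- b: share of patients using a rash/itch supportive drug at Week 0.
- f: share of those users free under the protocol to stop.
- s: share of the free users who would stop by a given visit because the rash improved.
- g: share of non-users free under the protocol to start a rash/itch drug.
- t: share of those free non-users who would start.
- o: share counted only because of a drug for another indication.

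**Formula.** Ignoring dropout, the rash/itch part at a later visit is

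R = b(1 − f·s) + (1 − b)·g·t,

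and the reported proportion is P = R + o. An effect of benralizumab on the rash acts through s and t. The medication rules act through f and g.

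**Cases.**

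1. *Both rules followed, with Section 6.2 applied on study.* f and g are close to 0, so R is close to b for any s and t. They are not exactly 0, because Section 6.1 says should and covers only use of at least 7 days.
2. *Neither rule binding.* With f = g = 1, R = b(1 − s) + (1 − b)t, and the full change is visible.
3. *Some users free to stop, no starts.* R falls by b·f·s. The visible fall is scaled down by f, and f depends on how Sections 6.1 and 15.0 are read together for each patient.
4. *Only added drugs counted, in line with Section 1.0.* Baseline use drops out. What remains is new rash/itch treatment, which Section 6.2 holds near zero if it applies on study. The rule again largely sets the result.

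**Two further features.**

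- A dose reduction that stops short of zero leaves the patient in the count, so a binary proportion does not register it.
- o is free to move. Section 13.2 foresees higher-dose steroids or other immunosuppressants for additional irAEs, and both classes are in the Section 14 list. With no indication recorded in the summary, a change in o cannot be told apart from a change in R.

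**Sections 6.1 and 15.0 side by side.** Section 6.1 asks for continued use and does not mention dose. Section 15.0 rules out abrupt stopping at initiation and foresees gradual reduction where appropriate. A patient on a reduced dose is still using the drug, so the two agree until the taper would end in stopping. Past that point they pull apart for rash/itch corticosteroids, and no text says which governs.

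**Size.** The change hidden by the rules is the difference between cases 2 and 1, which is (1 − b)t − b·s. Its components are all unknown, so any number would only restate an assumption.

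**The case against.** The strongest defence has four parts.

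*The rules are softer than they look.* Section 6.1 says should and does not bind users of less than 7 days. The Section 6.2 line sits in a list of entry criteria, while the first item of that list does state a period. This stands. An on-study ban is a plausible reading, not settled text. But if the rules are loose, movement in the proportion mixes how they were applied with any effect on the rash.

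*The proportion can move.* A reader might infer that it is fixed and cannot show any change. The documents do not support that. Section 13.2 foresees on-study steroids and immunosuppressants for other irAEs, Section 15.0 foresees reductions, and patients who stop benralizumab leave the Week 16 to 32 visits for the follow-up visit, which changes who is counted. What holds is narrower: the rash/itch part is largely held at its entry level if the rules are followed.

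*Sections 6.1 and 15.0 can be followed together.* A reader might also infer a flat contradiction. That is too strong, because the conflict is clear only where a taper would end in stopping.

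*The summary is descriptive, and stable background medication has a purpose.* No test, threshold or sparing claim is planned, the trial has a single arm, and holding background treatment steady protects the Week 4 primary response from confounding. This is a fair reason for having such rules. It does not make the proportion a measure of need, and the trade-off should be stated next to the endpoint.

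**Conclusion.** The point holds in this form. The Section 14 proportion separates neither baseline from new use nor rash/itch treatment from other indications. If Sections 6.1 and 6.2 are followed, its rash/itch part stays largely at its entry level whether or not benralizumab works. It is therefore a poor measure of the additional supportive care named in Section 1.0. Use for other irAEs can move the total, but that movement says nothing about the rash.

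The conclusion assumes that the Section 6.1 rule is generally followed and, for new starts, that Section 6.2 applies during treatment. No numeric magnitude can be given because baseline use is not stated. The endpoint is descriptive and secondary. The change should be made before analysis, but the trial's main conclusion does not depend on it.

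**What to change.** **Reconcile the texts.** Sections 6.1, 6.2, 13.2, 14 and 15.0 should agree on whether rash/itch medication may be reduced, stopped or started on study, and Section 6.2 should state the period it covers. No position is taken here on which rule is right.

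**Replace the single proportion in Section 14.** Report the following by indication (ercAE versus other), from the concomitant-medication review:

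- (a) among all dosed patients, the proportion with a supportive drug newly started or escalated after Week 0/Day 1;
- (b) among users at Week 0, the proportion with the dose reduced or the drug stopped.

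**State the limits that follow from the rules kept.** If the continuation rule stays, say that the trial cannot assess stopping of these drugs. If the bar on new drugs applies on study, report rash/itch new starts as departures from it and do not read a low rate as benefit.

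**Cost.** Protocol wording and a revised summary table. The visit-by-visit review already exists, though indication, dose and start/stop dates must be usable from it. The main downside is the smaller denominator for (b), and so a wider interval.
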